10.0 CRITERIA FOR EVALUATION AND ENDPOINT DEFINITIONS

Measurement of Effect

10.1 Progression/Relapse

Appearance of any new lesion/site. Death due to disease without prior documentation of progression.

- Appearance of a new melanoma in-situ or Stage I melanoma which can be treated curatively by wide excision does not constitute recurrence. If this does occur, upload pathology and operative reports via the Source Documentation: Follow-Up Form in Rave.
- In cases for which initial flare reaction is possible (hypercalcemia, increased bone pain, erythema of skin lesions), either symptoms persist beyond 4 weeks or there must be additional evidence of progression.
- For bone disease documented on bone scan only, increased uptake does not constitute unequivocal progression. However, increase in the soft tissue component of a lesion as measured by CT or MRI would constitute progression.
- Appearance of new pleural effusions does not constitute unequivocal progression unless cytologically proven of neoplastic origin, since some effusions are a toxicity related to therapy or other medical conditions. Increase in the size of an existing effusion does not constitute unequivocal progression, since the fluid status of the patient could alter the size of the effusion.

Notes regarding new lesions: FDG-PET imaging can complement regular scans in identifying new lesions according to the following algorithm.

- 1) Negative FDG-PET at baseline, with a positive FDG-PET at follow-up is a sign of progression based on a new lesion.
- 2) No FDG-PET at baseline and a positive FDG-PET at follow-up corresponding to a potential new site of disease must have a confirmation by anatomical assessment (e.g. CT, MRI, X-ray) as new site of disease to be considered progressive disease. In such a case, the date of progressive disease will be the date of the initial abnormal FDG-PET.

10.2 Relapse-Free Survival

Measured from date of randomization to date of first documentation of relapse or death due to any cause. Patients last known to be alive and relapse-free are censored at date of last contact.

10.3 Overall Survival

Measured from date of randomization to date of death due to any cause. Patients known to be alive are censored at date of last contact.

10.4 Performance Status

Patients will be graded according to the Zubrod Performance Status Scale.

POINT	DESCRIPTION
0	Fully active, able to carry on all pre-disease performance without restriction.
1	Restricted in physically strenuous activity but ambulatory and able to carry out work of a light or sedentary nature, e.g., light housework, office work.
2	Ambulatory and capable of self-care but unable to carry out any work activities; up and about more than 50% of waking hours.
3	Capable of limited self-care, confined to bed or chair more than 50% of waking hours.
4	Completely disabled; cannot carry on any self-care; totally confined to bed or chair.

11.0 STATISTICAL CONSIDERATIONS

11.1 Accrual goals

Based on E1609, an intergroup accrual rate of at least 45 patients per month is assumed.

It is assumed that up to 10% of patients will be ineligible. It is expected that 1378 registered patients will be required to accrue 1,240 eligible patients (see below for sample size calculations). Including time to ramp up accrual, it is anticipated that it will take less than 2.5 years to complete accrual for this trial.

11.2 Overall survival (OS) and relapse-free survival (RFS) objectives

There are three primary objectives of this study: 1) to test whether OS is improved with pembrolizumab compared to a control arm of physician/patient choice of high-dose interferon (HDI) or ipilimumab in this patient population, 2) to test whether among patients who are PD-L1 positive OS is improved with pembrolizumab compared to this control arm in this patient population, 3) to test whether RFS is improved with pembrolizumab compared to this control arm in this patient population.

11.3 Overall survival (OS) and relapse-free survival (RFS) design assumptions

OS and RFS estimates from S0008 indicate that a proportion of patients may be long-term survivors in the sense that they will not be observed to relapse or die during the follow-up period planned for the study. It is further assumed that there are no differences in OS or RFS between the treatment regimens in the control arm.

An exponential cure rate model fit to OS on the HDI arm of S0008 indicated that 40% of patients were long-term survivors and that median OS for patients who were not long-term survivors was 3.01 years (null hypothesis). The null OS model is written that the OS at year t is equal to $0.40 + 0.60 \cdot \exp(-0.23t)$. For sample size calculations, it is assumed that OS with pembrolizumab will also follow an exponential cure rate model, but with 45% of patients long-term survivors and a median OS for non-long term survivors of 3.96 years (alternative hypothesis). The alternative OS model is written that the OS at year t is equal

to $0.45+0.55*\exp(-0.175t)$. This corresponds to an average hazard ratio (HR, average of 10,000 simulated hazard ratios from the Cox model) of 0.73 from a Cox proportional hazards model at 100% OS events (374 events at Study Year 5).

An exponential cure rate model fit to RFS on the HDI arm of **S0008** indicated that 35% of patients were long-term survivors and that median RFS for patients who were not long-term survivors was 1.03 years (null hypothesis). The null RFS model is written that the RFS at year t is equal to $0.35+0.65*\exp(-0.67t)$. For sample size calculations, it is assumed that RFS with pembrolizumab will also follow an exponential cure rate model, but with 41% of patients long-term survivors and a median RFS for non-long term survivors of 1.44 years (alternative hypothesis). The alternative RFS model is written that RFS at year t is equal to $0.41+0.59*\exp(-0.48t)$. This corresponds to an average hazard ratio (HR) of 0.70 from a Cox proportional hazards model at 100% RFS information.

We assume a total two-sided alpha of 5% (one-sided alpha of 2.5%) allocated between the four co-primary objectives as detailed below. We assume 1:1 randomization, 2.5 years of accrual, 2.5 years of follow-up after accrual completes. We assume 48.2% of patients will be PD-L1 positive, (based on the lower limit of the 95% confidence interval of the prevalence from ClinicalTrials.gov trial NCT 01704287), 46.8% will be PD-L1 negative, and 5% will be PD-L1 indeterminate. All testing will be stratified by the randomization stratification. Tests of the null hypothesis will be done using the log-rank test. Futility analysis testing will be performed using a modified log-rank test modified for testing non-null hypotheses (a score test of the alternative hazard ratio).

11.4 Alpha allocation between Overall survival (OS) and Relapse-free survival (RFS)

Using a Bonferroni split, 4.6% (two-sided) of the alpha will be allocated to the OS endpoint (overall population and PD-L1+ subgroup) and 0.4% (two-sided) of the alpha will be allocated to the RFS endpoint (overall population). For OS, 80% of the alpha will be allocated to the overall population and the remaining alpha will be allocated to the PD-L1 positive subgroup using the method described in the next paragraph.

Under the null hypothesis, the test statistics for the overall population and the PD-L1 positive subgroups are multivariable normal with correlation equal to the proportion of events the PD-L1 positive subgroup relative to the whole population. (25) The residual alpha for the PD-L1 population can be calculated using this relationship. For clarity in the exposition of the design we will assume the PD-L1 positive subgroup has 48.2% of the total OS events of the study (based on the lower limit of the 95% confidence interval of the prevalence from ClinicalTrials.gov trial NCT 01704287). For the final analyses involving the PD-L1 positive subgroups, the actual alpha level will be calculated using the multivariate normal relationship based on the PD-L1 positive proportion observed in the trial

Under these assumptions, the alpha allocation is expected to be as follows: the OS overall population with 3.7% (two-sided) and the PD-L1 + subgroup OS with 1.52% (two-sided). Accounting for the correlation between the subgroup and overall group, the overall alpha is 4.6% (two-sided) for OS and 0.4% (two-sided) for RFS.

- OS overall population 3.7%
- OS PD-L1 + subgroup 1.52%
- RFS overall population 0.4%

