¹ Alpha to be calculated based on observed proportion of total OS events in the PD-L1 positive group.

The sample size of this trial was determined to ensure appropriate power to detect meaningful OS differences. As such, the trial is overpowered for RFS, and may therefore detect small RFS differences of uncertain clinical benefit. Hence, regardless of the statistical significance of the RFS results, the clinical benefit of pembrolizumab will be

assessed by the magnitude of the relative and absolute RFS improvement of the pembrolizumab arm over the control arm, and by the comparisons of overall survival and toxicity between the treatment arms.

Under this design and assuming PD-L1 positive patients have the same OS on the control arm as the whole population, the alternative OS survival model for 80% power is model is written that OS at year t is equal to $0.44+0.56\exp(-0.13t)$ [44% long-term survivors and median OS of 5.3 years for non-long-term survivors]. This corresponds to an average HR of 0.58 from a Cox proportional hazards model at 100% OS events. The alternative OS survival model for 90% power is model is written that OS at year t is equal to $0.45+0.55\exp(-0.13t)$ [45% long-term survivors and median OS of 5.3 years for non-long-term survivors]. This corresponds to an average HR of 0.56 from a Cox proportional hazards model at 100% OS events.

Design properties were determined via simulation with 100,000 replications. Properties of the design are summarized in the tables below.

Table 1 Overall population OS Interim and final analysis summary. Events calculated across both arms. Actual analysis timing may vary.

Percent OS events	Study Year	N events	Tests done
55%	3	206	Efficacy and futility
80%	4	299	Efficacy and futility
100%	5	374	Efficacy

Table 2 Characteristics of interim and final overall population OS analyses

OS Scenario	Probability under alternative	Probability under null
Probability stop for futility at 1 st interim analysis	1%	50%
Probability stop for efficacy at 1 st interim analysis	28%	<1%
Probability stop for futility at 2 nd interim analysis	1%	17%
Probability stop for efficacy at 2 nd interim analysis	19%	<1%
Probability stop early for futility	2%	67%
Probability stop early for efficacy	48%	1%
Probability of positive result	86%	2.1% ^a

^a Ignoring futility monitoring two-sided, alpha level=3.7%

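### The written rule for the PD-L1 positive OS alpha takes the event share as the correlation, not its square root, so applying it at the final analysis gives 1.14% instead of the planned 1.52%

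*Combined protocol and SAP*

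**What the plan says.** Section 11.4 first divides alpha between endpoints: "Using a Bonferroni split, 4.6% (two-sided) of the alpha will be allocated to the OS endpoint", with 0.4% left for relapse-free survival. Within OS, "For OS, 80% of the alpha will be allocated to the overall population", and the PD-L1 positive subgroup gets what remains once the correlation between the two tests is allowed for. The two statistics, it says, "are multivariable normal with correlation equal to the proportion of events the PD-L1 positive subgroup relative to the whole population".

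For planning, "we will assume the PD-L1 positive subgroup has 48.2% of the total OS events of the study". On that basis the section reports two-sided levels of 3.7% (overall OS) and 1.52% (PD-L1 positive OS), which together spend 4.6%.

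The 1.52% is a planning value. For the final analysis, Section 11.4 says "the actual alpha level will be calculated using the multivariate normal relationship based on the PD-L1 positive proportion observed in the trial". A footnote in Section 11.5 reads "Alpha to be calculated based on observed proportion of total OS events in the PD-L1 positive group", and the note under Table 7 likewise refers to the observed fraction of events. No section mentions a square root.

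**The concern.** The subgroup and overall log-rank statistics share the subgroup's events. Their correlation is the square root of the subgroup's share of the information, not the share itself. A correlation that is too low makes the two tests look closer to independent than they are, so the residual alpha comes out too small.

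OS in PD-L1 positive patients is a primary objective (Section 1.1b), and its threshold depends on this one sentence. If the observed event share differs from 48.2%, the printed 1.52% no longer applies and the analyst has to return to the written rule. At the planned share, a subgroup p-value between 0.0114 and 0.0152 would be significant under one reading and not under the other. Choosing the formula after the data are seen would be hard to defend.

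There is a smaller looseness in the input. The last sentence of the rule in Section 11.4 speaks of the PD-L1 positive proportion, which can be read as patients. The Section 11.5 footnote and the Table 7 note speak of events. The two differ if PD-L1 status is prognostic.

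**Working it through.** **Inputs.** Total OS alpha 4.6%, overall OS alpha 3.7% (80% × 4.6% = 3.68%, rounded up in the plan) and PD-L1 positive event share 48.2%, all from Section 11.4. Final OS events 374 (Section 11.3). Interim looks at 206 and 299 events, each at one-sided 0.125%, and a final one-sided level of 1.8% (Section 11.5 and its tables).

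**Why the square root.** All testing is stratified by the randomization factors (Section 11.5), and PD-L1 status is one of them (Section 6.0). The stratified overall score is therefore U_all = U_sub + U_rest, with the two parts independent. Under the null:

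- Cov(U_sub, U_all) = V_sub
- Corr = V_sub / √(V_sub × V_all) = √(V_sub / V_all) ≈ √(event share)

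With a share of 0.482 the correlation is √0.482 = 0.694.

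**Solving for the residual alpha.** Find a such that, for a standard bivariate normal pair with correlation ρ,

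P(Z₁ > z for 1.85% or Z₂ > z for a/2) = 2.3% one-sided (4.6% two-sided).

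| Correlation used | Residual two-sided alpha a |
|---|---|
| √0.482 = 0.694 | 1.518% (the plan's 1.52%) |
| 0.482, as written | 1.141% |

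The two-sided version of the equation gives the same values.

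**Working backwards.** The correlation implied by 3.7%, 1.52% and 4.6% is 0.695, and 0.695² = 0.483. The design figure was computed with the square root. If the correlation really were 0.482, then 3.7% and 1.52% together would spend 4.92%, more than the 4.6% allotted.

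**Sensitivity to the overall alpha.** With 3.68% for overall OS the residual is 1.54% (square root) against 1.16% (as written). With 3.6% it is 1.65% against 1.25%. No variant with a correlation of 0.482 reaches 1.52%.

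**Alpha left unspent.** Testing at 3.7% and 1.14% when the true correlation is 0.694 spends 4.34%, so 4.6% − 4.34% = 0.26 percentage points go unused. A simulation that includes the two interim looks (20 million replicates) gives OS totals of 4.58% with 1.52% and 4.32% with 1.14%.

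**Other event shares (overall OS alpha 3.7%).**

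| PD-L1 positive share of OS events | As written | Square root |
|---|---|---|
| 30% | 1.00% | 1.22% |
| 48.2% | 1.14% | 1.52% |
| 50% | 1.16% | 1.56% |
| 60% | 1.31% | 1.80% |
| 70% | 1.54% | 2.12% |
| 80% | 1.92% | 2.59% |
| 90% | 2.64% | 3.30% |

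The shares far from 48.2% are illustrative. The written rule is lower at every one.

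**Power.** Schoenfeld approximation, power = Φ(−ln(HR) × √d / 2 − z for a/2), with d = 0.482 × 374 ≈ 180 PD-L1 positive events:

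| HR | At 1.52% | At 1.14% |
|---|---|---|
| 0.57 | 91.1% | 89.3% |
| 0.58 | 89.1% | 87.0% |
| 0.73 (the overall alternative) | 37.6% | 33.8% |

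A stronger subgroup effect would leave fewer than 180 events. With 160 events and HR 0.58, power falls from 84.6% to 82.0%. Simulated trials of 596 patients under the plan's 44% long-term-survivor alternative gave 87.7% falling to 85.4%.

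**The case against.** The best defence is that this is a wording slip and not a design error. The 1.52% was computed correctly and appears consistently in Section 11.4, in the text of Section 11.5, in Table 7 and in the explanation below it. A statistician who checks the recalculation against those figures, or against the required 4.6% total, would see that 0.482 does not fit. Even on the literal reading the error is conservative. Familywise error falls, and the overall OS level, the relapse-free survival level, the sample size and the analysis timing are untouched.

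Most of that stands. The tables are right, nothing is inflated, and the power cost at the plan's own subgroup alternatives is about 2 points. The loss of about 4 points arises only if the subgroup effect equals the overall alternative, for which the subgroup test was not powered. The power levels above also exceed the 80% that Section 11.5 attaches to the 44% alternative, so the differences should be relied on, not the levels. The looseness between patients and events is minor, since Section 11.4 itself defines the rule on events and the Table 7 note confirms it.

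What does not stand is the inference that the text can be left alone. The plan commits to recalculating the level, the sentence is the only statement of how, and nothing directs the analyst to the square root.

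**Conclusion.** The rule is wrong as written and contradicts the alpha stated in the same section. At the planned 48.2% event share it gives 1.14% instead of 1.52%, leaves about 0.26 percentage points of OS alpha unspent, and costs about 2 points of power in the PD-L1 positive test. The actual figure will depend on the observed event share.

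The conclusion rests on the plan's own allocation (3.7% within 4.6%) and on the usual approximation that log-rank information is proportional to events. The practical effect is conditional on the final calculation following the text. Because the text fixes the significance threshold for a primary objective, it should be corrected before that analysis.

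**What to change.** In Section 11.4, state that the correlation equals the square root of the proportion of OS events that occur in the PD-L1 positive subgroup. Change the closing sentence of that paragraph so that the final alpha is based on the observed proportion of OS events in the PD-L1 positive subgroup, in line with the Section 11.5 footnote and the Table 7 note.

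The cost is a correction to two sentences. At the planned 48.2%, the alpha of 1.52% and the tables that use it stay as they are, and total OS alpha remains 4.6%. The change should be dated before the final OS data are examined.

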11.5 Interim and final analysis plans

The primary analysis will be intent-to-treat population.

All testing will be stratified by the randomization stratification factors. Tests of the null hypothesis will be done using the log-rank test. Futility analysis testing will be performed using a modified log-rank test modified for testing non-null hypotheses (a score of the alternative hazard ratio).

100% of expected RFS is 536 events. One formal interim analysis of the overall population RFS endpoint is scheduled at approximately 75% of RFS events (402 RFS events calculated across both arms under the alternative). At the interim analysis, an efficacy test will be done (test of null hypothesis $HR=1$) with a one-sided alpha=0.09%. At the interim analysis a futility test will evaluate if the HR from a Cox regression model stratified by the randomization factors favors the control arm ($HR>1$). If an efficacy or futility boundary is crossed at the interim analysis, the DSMC will consider early release of the RFS results. The final analysis of the overall population RFS will test of the null hypothesis ($HR=1$) at the two-sided 0.32% level (one-sided 0.16% level) in order to account for the interim analysis.

Up to two formal interim analyses of the overall population OS will be completed at approximately 55% and 80% events (206 and 399 events, respectively, events calculated across both arms under the alternative). At both interim analyses, an efficacy test will be done (test of null hypothesis $HR=1$) with a one-sided alpha=0.125%. At the first interim analysis a futility test will evaluate if the HR from a Cox regression model stratified by the randomization factors favors the control arm ($HR>1$). At the second interim analysis a futility test will be done testing the alternative hazard ratio ($HR=0.73$) with a one-sided alpha of 2.5%. If a boundary for futility is crossed at an interim analysis, the DSMC will consider the toxicities on each arm. Considering the magnitude of the survival difference between the two arms along with the relative toxicities, the DSMC can choose not to recommend reporting results early if additional data on the potential non-inferiority of pembrolizumab is warranted. The final analysis of the overall population OS will test of the null hypothesis ($HR=1$) at the two-sided 3.6% level (one-sided 1.8% level) in order to account for interim analyses. At the final analysis for the overall population OS, a two-sided test of the null hypothesis of OS in the PD-L1 positive subgroup will be performed at the two-sided alpha=1.52% level² (one-sided 0.76% level).

The final OS superiority test will be performed in a stepwise fashion following an OS non-inferiority test using a margin of 1.045. An upper limit of a one-sided 98.15% confidence interval less than 1.045 will be considered evidence of non-inferiority of pembrolizumab compared to the control arm.

At the final analysis for OS, results for RFS with updated follow-up will be presented. We note that because of the expected survival patterns with this population, the average hazard ratio is expected to become more null (closer to 1) over time. Under the alternative hypothesis, at 3.5 years since the first patient is randomized the hazard ratio is 0.70, while at 5 years since the first patient is randomized the hazard ratio is 0.73.

There will be no formal interim testing of RFS (overall or PD-L1 positive subgroup) or of OS in the PD-L1 positive subgroup.

If 100% RFS or OS events has not been reached by 3.5 years after the last eligible patient is randomized, the final RFS and OS analyses will be performed at this time.

¹ Alpha to be calculated based on observed proportion of total OS events in the PD-L1 positive group.

The sample size of this trial was determined to ensure appropriate power to detect meaningful OS differences. As such, the trial is overpowered for RFS, and may therefore detect small RFS differences of uncertain clinical benefit. Hence, regardless of the statistical significance of the RFS results, the clinical benefit of pembrolizumab will be

assessed by the magnitude of the relative and absolute RFS improvement of the pembrolizumab arm over the control arm, and by the comparisons of overall survival and toxicity between the treatment arms.

Under this design and assuming PD-L1 positive patients have the same OS on the control arm as the whole population, the alternative OS survival model for 80% power is model is written that OS at year t is equal to $0.44+0.56\exp(-0.13t)$ [44% long-term survivors and median OS of 5.3 years for non-long-term survivors]. This corresponds to an average HR of 0.58 from a Cox proportional hazards model at 100% OS events. The alternative OS survival model for 90% power is model is written that OS at year t is equal to $0.45+0.55\exp(-0.13t)$ [45% long-term survivors and median OS of 5.3 years for non-long-term survivors]. This corresponds to an average HR of 0.56 from a Cox proportional hazards model at 100% OS events.

Design properties were determined via simulation with 100,000 replications. Properties of the design are summarized in the tables below.

Table 1 Overall population OS Interim and final analysis summary. Events calculated across both arms. Actual analysis timing may vary.

Percent OS events	Study Year	N events	Tests done
55%	3	206	Efficacy and futility
80%	4	299	Efficacy and futility
100%	5	374	Efficacy

Table 2 Characteristics of interim and final overall population OS analyses

OS Scenario	Probability under alternative	Probability under null
Probability stop for futility at 1 st interim analysis	1%	50%
Probability stop for efficacy at 1 st interim analysis	28%	<1%
Probability stop for futility at 2 nd interim analysis	1%	17%
Probability stop for efficacy at 2 nd interim analysis	19%	<1%
Probability stop early for futility	2%	67%
Probability stop early for efficacy	48%	1%
Probability of positive result	86%	2.1% ^a

^a Ignoring futility monitoring two-sided, alpha level=3.7%

Table 3 Overall population RFS Interim and final analysis summary. Events calculated across both arms. Actual analysis timing may vary.

Percent RFS events	Expected time	N events	Tests done
75%	Mid-2018	402	Efficacy and futility
100%	Late 2018	536	Efficacy

Table 4 Characteristics of interim and final overall population RFS analyses

RFS Scenario	Probability under alternative	Probability under null
Probability stop for futility at interim analysis	<1%	50%
Probability stop for efficacy at interim analysis	69%	<1%
Probability of positive result	90%	0.22% ^a

^a Ignoring futility monitoring two-sided, alpha level=0.4%

Table 5 Additional characteristics of overall population OS analyses. Events calculated across both arms. Actual analysis timing may vary.

Analysis	Alpha level	HR threshold	OS Events
Year 3 interim efficacy	0.125% (one-sided)	0.67	206
Year 3 interim futility	NA	1	206
Year 4 interim efficacy	0.125% (one-sided)	0.70	299
Year 4 interim futility	2.5%	0.92	299
Year 5 final efficacy	3.6% (two-sided)	0.81	374

HR threshold = HR that will correspond to a significant p-value based on alpha level. For efficacy analyses HRs less than the threshold will be significant, for futility analyses HRs larger than the threshold will warrant early closure of the study.

Table 6 Characteristics of overall population RFS analyses. Actual analysis timing may vary.

Analysis	Alpha level	HR threshold	RFS Events
interim efficacy	0.09% (one-sided)	0.66	402
Interim futility	NA	1	402
Final efficacy	0.32% (two-sided)	0.78	536
Year 5 follow-up	NA	NA	668

HR threshold = HR that will correspond to a significant p-value based on alpha level. For efficacy analyses HRs less than the threshold will be significant.

Table 7 PD-L1 positive subgroup analysis details, N = 596 (48.2% prevalence)*

Endpoint	Time point	Alpha-level (two sided)*	HR threshold	Design HR	Power
OS	Year 5	1.52%	0.66	0.57	80%
OS	Year 5	1.52%	0.68	0.56	90%

* These calculations assume a 48.2% event fraction in the PD-L1 positive subgroup. For the final analysis, calculations will be based on the observed fraction of events in the trial. HR threshold = HR that will correspond to a significant p-value based on alpha level. Design HR = HR that provides stated level of power.

How to interpret the first line of [Table 7](#): If 48.2% of patients are PDL1-positive (and making all the assumptions about survival in the protocol), at Year 5 we will have 80% power to detect a true hazard ratio of 0.57 for OS. In other words, if the true hazard ratio between the arms is 0.57 and we ran the trial many times, 80% of the trials would have an observed hazard ratio of 0.62 or less or a two-sided p-value less than 0.0152.

11.6 Anticipated stage distribution.

Eligibility for SWOG trial [S0008](#) included Stages IIIA(n2), IIIB, and IIIC. Eligibility for ECOG trial [E1609](#) included Stages IIIB, IIIC, M1a, and M1b. Eligibility for this trial [S1404](#) includes Stages IIIA(n2), IIIB, IIIC, M1a, M1b, and M1c. Null (historical) survival estimates for [S1404](#) are based on [S0008](#) data. We note that compared to [S0008](#), [S1404](#) will also include M1a, M1b, and M1c patients. In [E1609](#) 6% of patients were Stage M1a and 2% were M1b. We expect approximately 1% of randomized patients to be Stage M1c. We expect less than 10% of randomized patients in [S1404](#) to be Stage M1, and because of modest differences in expected survival we have used [S0008](#) survival patterns as a historical reference for this trial.

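### Four null-column entries in the OS operating-characteristics table (Table 2) do not follow from the stated stopping rules, and the text prints 399 events for the second interim where 299 is meant

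*Combined protocol and SAP*

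**What the plan says.** Section 11.5 sets the overall-population OS interims "at approximately 55% and 80% events (206 and 399 events, respectively, events calculated across both arms under the alternative". Table 1 gives the second look as "80% 4 299 Efficacy and futility" (percentage, study year, events, tests), Table 5 also uses 299, and both tables put the final analysis at 374 events.

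The text fixes the decision rules. Efficacy is tested at one-sided 0.125% at each interim and at one-sided 1.8% (two-sided 3.6%) at the final analysis. The futility criterion is HR above 1 at the first look. At the second look it is a one-sided 2.5% test of HR 0.73, which Table 5 translates to a cut at 0.92.

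Table 2 reports the consequences, with the alternative first and the null second in each row: "Probability stop early for futility 2% 67" per cent, "Probability stop early for efficacy 48% 1" per cent and "Probability of positive result 86% 2.1" per cent. The separate row for second-look futility gives 17% under the null. A footnote to the 2.1% reads "Ignoring futility monitoring two-sided, alpha level=3.7" per cent. The source is given as "Design properties were determined via simulation with 100,000 replications". On futility, the text adds that "the DSMC can choose not to recommend reporting results early".

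**The concern.** A second interim at 399 events would fall after the 374-event final analysis, so the text contradicts its own 80% and both tables.

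Table 2 shows three signs of inconsistency before any modelling:

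- Two looks at one-sided 0.125% cannot give more than 0.25% early efficacy under the null, yet the table prints 1%.
- The footnote's 3.7% two-sided is 1.85% one-sided. Futility stopping can only lower the chance of a positive result, yet the table prints 2.1%.
- A futility cut at HR 0.92, on the favourable side of 1, should catch most null trials by the second look, which makes 67% look low.

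Table 2 is the plan's account of how the design behaves for its main primary endpoint. If the table and the rules disagree, a reader or the DSMC cannot tell which rule was intended. The chance of a futility signal for an ineffective treatment is also misstated.

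**Working it through.** **Inputs.** From Sections 11.1, 11.3 and 11.5: looks at 206, 299 and 374 events; the efficacy and futility rules above; null OS 0.40 + 0.60·exp(−0.23t); alternative OS 0.45 + 0.55·exp(−0.175t); 1:1 allocation; 1,240 eligible patients; 2.5 years of accrual and 2.5 years of follow-up.

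**Event count.** 0.80 × 374 = 299.2, which agrees with Tables 1 and 5. 399/374 = 107%.

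**HR thresholds.** With d events, the log-rank Z is about −ln(HR)·√d/2, so an efficacy threshold is exp(−2z/√d).

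- 206 events, z = 3.023: 0.656 (Table 5 prints 0.67)
- 299 events, z = 3.023: 0.705 (0.70)
- 374 events, z = 2.097: 0.805 (0.81)
- Second-look futility: 0.73·exp(1.96 × 2/√299) = 0.916 (0.92)

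An HR of 0.67 at 206 events has one-sided p = 0.0020, so it would miss the stated 0.125%.

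**Alternative column, to validate the method.** Two patient-level simulations used the plan's cure models, uniform accrual and unstratified log-rank tests.

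| Alternative | Table 2 | 12,000 trials | 6,000 trials |
|---|---|---|---|
| Futility, look 1 | 1% | 0.6% | 0.7% |
| Efficacy, look 1 | 28% | 28.9% | 27.4% |
| Futility, look 2 | 1% | 1.2% | 1.2% |
| Efficacy, look 2 | 19% | 19.5% | 19.2% |
| Any early efficacy | 48% | 48.4% | 46.5% |
| Positive result | 86% | 85.5% | 85.6% |

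**Null column.** The three Z statistics are jointly normal with mean 0 and correlation √(dᵢ/dⱼ).

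A lower bound can be had by hand. HR above 0.916 at 299 events means Z₂ < −ln(0.73)·√299/2 − 1.96 = 2.721 − 1.960 = 0.761, which has null probability 77.7%. Apart from a negligible early-efficacy overlap, every such trial has crossed a futility boundary by the second look. The total must therefore be at least about 77.7%, already well above 67%.

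Exact integration gives:

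- Efficacy: 0.125% at look 1, a further 0.086% at look 2, 0.211% at either.
- Positive result ignoring futility: 1.842% one-sided, or 3.68% two-sided. This rounds to the footnote's 3.7%. With binding futility it is 1.83%.
- Futility: 50.0% at look 1 and 28.7% at look 2, total 78.7%.

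| Null | Table 2 | Computed | 12,000 trials | 6,000 trials |
|---|---|---|---|---|
| Futility, look 2 | 17% | 28.7% | 29.0% | 28.8% |
| Any futility crossing | 67% | 78.7% | 79.0% | 78.2% |
| Any early efficacy | 1% | 0.21% | 0.24% | 0.18% |
| Positive result | 2.1% | 1.84% | 1.65% | 1.92% |

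The patient-level runs are too small to settle the last row (standard error 0.12 points with 12,000 trials). That row rests on the exact calculation. The first-look rows under the null (50% and below 1%) and the second-look efficacy row (below 1%) do reproduce.

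**Other explanations tried.**

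- Simulation error: with 100,000 replications the standard error is √(0.287 × 0.713/100,000) = 0.14 points for 28.7% and 0.04 points for 1.84%.
- The printed cut of 0.92: 27.6% and 77.6%.
- Table 5's unlabelled 2.5% read as two-sided (cut 0.946): 21.1% and 71.1%.
- Null event counts at calendar years 3, 4 and 5 (240/343/426): 33.4% at look 2.
- A second look at 399 events: 38.8%.

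To obtain 17%, the cut against 0.73 must be about HR 0.963 (one-sided 0.8%). To obtain 2.1%, the final one-sided level must be about 2.06%. The plan states neither.

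**The case against.** The best case on the other side is that nothing governing the trial is wrong. The 399 corrects itself, since the sentence says 80% and both tables print 299. Efficacy decisions rest on the stated alpha levels, the second-look futility cut in Table 5 is right, and Table 2 is descriptive. Futility is advisory, so neither 67% nor 79% is the share of null trials that would stop. The document is Revision 17, dated November 2023, and refers to enrolment in the past tense, so design-stage probabilities can no longer inform design choices. The 1% cell may be two entries of below 1% added and rounded up. The patient-level check was unstratified, whereas the plan's tests are stratified.

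Much of this stands as a limit on importance. Error control and power are intact, the 1% cell and the 0.67 threshold are minor, and 79% is a crossing probability. The cause of the mismatch cannot be identified either: a futility level near 0.8% gives 17%, and a tested HR near 0.77 gives 16.3% and 66.3%. None of it reconciles 17%, 67% or 2.1% with the written rules. The null calculation uses only the event counts and boundaries, and stratification was not advanced as closing a gap of this size.

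**Conclusion.** The point holds. The second OS interim should read 299 events. Four null entries in Table 2 are inconsistent with the stated design: second-look futility 17% against 28.7% (27.6% at the printed 0.92); any futility crossing 67% against 78.7% (77.6%); early efficacy 1% against 0.21%; positive result 2.1% against 1.84% one-sided. The 2.1% also conflicts with the table's own footnote. Table 5's first-look efficacy threshold should be 0.66 rather than 0.67.

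The figures assume looks at exactly 206, 299 and 374 events and the usual normal approximation for the log-rank statistic. The stated boundaries spend 3.68% two-sided, within the 3.7% allocation, so type I error is not inflated, and power and sample size are unaffected. This is a reporting error in the operating characteristics of a primary endpoint and should be corrected.

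**What to change.** - In Section 11.5, change 399 to 299.
- Rerun the null column of Table 2 under the stated rules and print the result. Expect futility of about 50% at the first look, 29% at the second and 79% in total, early efficacy below 1%, and a positive result of about 1.8% one-sided. If a different rule was intended, state it and bring the text and Table 5 into line.
- Preferably, label the futility rows as boundary-crossing probabilities, because the DSMC may choose not to act.
- In Table 5, change the first-look efficacy threshold from 0.67 to 0.66.

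The cost is a correction of printed figures and one simulation rerun. Trial conduct does not change.
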